8.2.1 Adverse events of special interest

An AESI is any AE that a regulatory authority has mandated be reported on an expedited basis, regardless of the seriousness, expectedness, or relatedness of the AE to the administration of a UCB product/compound.

For ONC001, potential Hy's Law is used to identify AESIs and is defined using the laboratory data and the following potential drug-induced liver injury (PDILI) criteria:

- $\geq 3x$ upper limit of normal (ULN) alanine aminotransferase (ALT) *or* aspartate aminotransferase (AST) with coexisting $\geq 2x$ ULN total bilirubin in the absence of $\geq 2x$ ULN alkaline phosphatase (ALP), with no alternative explanation for the biochemical abnormality;
- Study participants who have evidence of liver metastases may be considered to have an alternate etiology for the described laboratory abnormalities.

All AESIs will be flagged on the listing of AEs.

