Screening Tests	Pregnancy tests: FSH and estradiol (for women of non-childbearing potential only); serum or urine hCG pregnancy test (for women of childbearing potential) Bone turnover markers: blood BAP, blood CTx, urinary NTx and urinary CTxII Tumor markers: e.g. PSA, CA125, CA19-9

ALP=alkaline phosphatase; ALT=alanine aminotransferase; aPTT=activated partial thromboplastin time; AST=aspartate aminotransferase; BAP=bone alkaline phosphatase; BUN=blood urea nitrogen; CA=cancer antigen; CRP=C-reactive protein; CTx=C-terminal telopeptide; FSH=follicle-stimulating hormone; GGT=gamma glutamyl transferase; hCG=human chorionic gonadotropin; INR=international normalized ratio; LDH=lactate dehydrogenase; MCH=mean corpuscular hemoglobin; MCHC=mean corpuscular hemoglobin concentration; MCV=mean corpuscular volume; NTx=N-terminal telopeptide; PSA=prostate specific antigen; RBC=red blood cell; WBC=white blood cell.

a including liver-specific ALP for use in assessing participants with bone metastases at Screening. In the case of bone metastases liver function abnormalities considered potential Hy's law cases, the liver-specific ALP must be separated from the total in participants with bone metastases and used to assess the liver function instead of the total ALP

The screening laboratory tests included above in [Table 8-1](#) will be listed only.

Liver function abnormalities will be defined using the following criteria:

- ALT or AST $\geq 2 \times \text{ULN}$
- ALT or AST $\geq 3 \times \text{ULN}$
- Total bilirubin $\geq 2 \times \text{ULN}$
- Total bilirubin $\geq 3 \times \text{ULN}$

- ALT or AST $\geq 5\times$ ULN
- ALT or AST $\geq 8\times$ ULN
- ALT or AST $\geq 3\times$ ULN AND total bilirubin $\geq 2\times$ ULN ($>35\%$ direct bilirubin)

For the subgroups of participants with liver metastases and without liver metastases at Baseline, the number and percentage of participants in each liver function abnormality category will be summarized at each visit.

In addition, participants with PDILI criteria are those that fulfill the following laboratory data (based on liver function tests) criteria at a visit:

- AST or ALT and total bilirubin within the normal range at Baseline and AST or ALT $\geq 3\times$ ULN concurrent with total bilirubin $\geq 2\times$ ULN;

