- AST, ALT or total bilirubin above ULN at Baseline and AST or ALT ≥ 2 times Baseline values AND AST or ALT $\geq 3\times$ ULN (participants without liver metastases at Baseline)/AST or ALT $\geq 8\times$ ULN (participants with liver metastases at Baseline) concurrent with total bilirubin above ULN at Baseline and total bilirubin ≥ 2 times Baseline value or $\geq 3\times$ ULN (whichever is lower).

All relevant laboratory data collected for participants with a PDILI event (i.e. liver function tests) will be listed at the visits at which at least one of the above criteria was fulfilled.

The number and percentage of participants meeting different combinations of the ALT, AST and total bilirubin criteria defined above will be summarized by treatment group. This summary will be presented for all participants as well as for the subgroups of participants who had liver metastases at Baseline and participants without liver metastases at Baseline.

A separate listing will also be produced containing drug-induced liver injury -relevant family medical history, lifestyle data (alcohol consumption or drug abuse in the previous 6 months), hepatic event supplemental medical history and any hepato-toxic medications taken for participants in the SS with a PDILI event.

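### The SAP gives the name PDILI criteria to two non-nested rules, so a Hy's Law AESI in a participant with raised Baseline liver tests can miss the dedicated PDILI listings

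*SAP*

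**What the plan says.** Section 8.2.1 states that potential Hy's Law "is used to identify AESIs and is defined using the laboratory data and the following potential drug-induced liver injury (PDILI) criteria". The rule is ALT or AST at least 3xULN together with total bilirubin at least 2xULN, without ALP at or above 2xULN, and with no other explanation. Baseline values play no part. On metastases it adds: "Study participants who have evidence of liver metastases may be considered to have an alternate etiology for the described laboratory abnormalities".

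Section 8.3 says that "participants with PDILI criteria are those that fulfill the following laboratory data (based on liver function tests) criteria at a visit", and gives two criteria:

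- Criterion 1 applies with "AST or ALT and total bilirubin within the normal range at Baseline" and then needs AST or ALT at least 3xULN concurrent with bilirubin at least 2xULN.
- Criterion 2 applies when AST, ALT or bilirubin was above ULN at Baseline. It needs AST or ALT at least twice Baseline, and at least 3xULN without liver metastases or 8xULN with them. Bilirubin must have been above ULN at Baseline and must reach the lower of twice Baseline and 3xULN.

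Neither criterion mentions ALP.

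Two outputs follow in 8.3. "All relevant laboratory data collected for participants with a PDILI event (i.e. liver function tests) will be listed at the visits" where at least one of the criteria just given was met. A separate listing of DILI-relevant family history, lifestyle data, supplemental hepatic history and hepatotoxic medication covers Safety Analysis Set participants with a PDILI event. Part C repeats both rules and both outputs under the same section numbers.

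**The concern.** One name covers two rules, and no text says how they relate. Section 8.2.1 makes AESI status depend on there being no alternative explanation. The second listing in 8.3 collects information that bears directly on that judgement: family history, alcohol or drug use, supplemental hepatic history and hepatotoxic drugs. If a participant meets 8.2.1 but not 8.3, the clinical study report can flag a Hy's Law AESI without setting this information beside it. A programmer also has no definition of *PDILI event* to work from, since both rules carry the PDILI name.

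**Working it through.** No sample size, power or error rate is involved. The check applies both rules to a few liver profiles. The thresholds come from SAP 8.2.1 and 8.3. The profiles are assumed for illustration, in multiples of ULN, and the transaminase figure is taken to hold for ALT and AST alike.

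Rules applied:

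- 8.2.1: transaminase >= 3, bilirubin >= 2, ALP < 2. The judgement on alternative explanations comes afterwards.
- 8.3 criterion 1: normal Baseline; transaminase >= 3; bilirubin >= 2.
- 8.3 criterion 2: any Baseline test > 1; transaminase >= 2 x Baseline and >= 3 (no metastases) or >= 8 (metastases); Baseline bilirubin > 1; bilirubin >= min(2 x Baseline, 3).

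| | Liver metastases | Baseline transaminase / bilirubin | On treatment transaminase / bilirubin / ALP | 8.2.1 thresholds | 8.3 |
|---|---|---|---|---|---|
| A | yes | 1.5 / 1.2 | 5 / 2.5 / 1.5 | met | not met |
| B | yes | 1.5 / 0.8 | 9 / 2.5 / 1 | met | not met |
| C | no | 1.5 / 0.8 | 5 / 2.5 / 1 | met | not met |
| D | no | 1.5 / 1.2 | 5 / 3 / 1 | met | met (criterion 2) |
| E | yes | 0.8 / 0.8 | 5 / 2.5 / 1 | met | met (criterion 1) |
| F | yes | 0.8 / 0.8 | 5 / 2.5 / 2.5 | not met (ALP) | met (criterion 1) |

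In A, B and C criterion 1 fails because Baseline is abnormal. Criterion 2 then runs as follows:

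- A: 5/1.5 = 3.3, so at least twice Baseline. Bilirubin must reach min(2 x 1.2, 3) = 2.4, and 2.5 does. The only failure is 5 < 8.
- B: 9 >= 8 and 9/1.5 = 6. Bilirubin must reach min(2 x 0.8, 3) = 1.6, and 2.5 does. The only failure is the clause "participants with liver metastases at Baseline) concurrent with total bilirubin above ULN at Baseline", since 0.8 is not above ULN.
- C: 5 >= 3, 5/1.5 = 3.3 and 2.5 >= 1.6. Again only the Baseline-bilirubin clause fails, here without metastases.

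D shows that a raised Baseline does not always lead to a miss. E shows that metastases with all-normal Baseline tests cause no gap: criterion 1 uses the same 3x and 2x multiples as 8.2.1 and no ALP condition, so it captures every such 8.2.1 case. F shows that the rules also differ in the other direction.

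The wording of criterion 1 on AST or ALT can mean both normal or either one normal. A to C fail under both readings. The readings do differ when only one transaminase is raised. With Baseline ALT 1.5, AST 0.9 and bilirubin 0.8, then ALT 5 and bilirubin 2.5, criterion 1 fails under the first and is met under the second.

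What remains available for A to C is given elsewhere in the SAP:

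| Information | Where presented regardless of PDILI status |
|---|---|
| ALT, AST, ALP, bilirubin | 8.3: listing of all chemistry data for anyone with an out-of-range value; separate listing of out-of-range results |
| Metastases and their location | 6.2 and 6.4 |
| Medical history | 6.5 |
| All medications | 6.6 |
| The AESI itself | 8.2 (table) and 8.2.1 (flag in the AE listing) |

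Sections 6 and 8 name no other output for DILI family history, the alcohol and drug-use data or the supplemental hepatic history. The focused laboratory extract and the identification of hepatotoxic drugs among all medications also belong only to the PDILI listings.

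**The case against.** The strongest reply is that most of the supporting data are listed anyway, as the last table shows. This stands. A reader might infer that the laboratory, history and medication data needed to judge the AESI would be absent; the SAP does not support that. Only the DILI-specific items and the focused presentation are at risk.

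Second, the history and medication listing is tied to a PDILI event, and 8.2.1 itself calls its rule PDILI criteria, so an 8.2.1 case might be included. This also stands: for that listing the trigger is ambiguous, and exclusion is not established. The laboratory listing, by contrast, is tied to the criteria in 8.3.

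Third, metastases may explain the abnormality. That provision is discretionary, so a case not attributed to metastases remains an AESI, and profile C has none. It does defeat the inference that every participant with metastases and ALT/AST between 3 and 8xULN falls in the gap. The Baseline tests must also be abnormal, bilirubin at least 2xULN and ALP below 2xULN, and no alternative explanation accepted.

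Fourth, a Hy's Law screen and a Baseline-adjusted laboratory screen may properly differ. Agreed: profile F simply reflects the ALP exclusion and is not in itself an error, and nothing in the SAP requires AESI and PDILI counts to match. Different purposes do not justify a shared name and an undefined trigger.

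**Conclusion.** The point holds as a gap in safety reporting of modest size. As written, a potential Hy's Law AESI with at least one raised Baseline liver test can fall outside the focused PDILI laboratory listing, and may fall outside the hepatic history and medication listing. With metastases the 8xULN requirement or the Baseline-bilirubin clause can cause this; without them the latter can.

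The conclusion rests on a literal reading of criterion 2 and on illustrative profiles. The documents give no frequency; with up to 27 participants in each part, cases may be few, though each would matter. They do not show that the case itself disappears from the report, and nothing here bears on which liver thresholds are right.

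**What to change.** In both Part B and Part C, reconcile 8.2.1 with 8.3:

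1. Give the 8.2.1 rule its own name, for example potential Hy's Law laboratory criteria, and keep PDILI for 8.3.
2. Define *PDILI event* explicitly.
3. Produce the focused laboratory listing and the hepatic history and medication listing for every participant who meets either rule, with a column showing which was met.

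No threshold is to be changed on account of this point. The cost is SAP wording, one extra flag and a few more listing rows.

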8.2.2 Infusion-related reactions

Infusion-related reactions are defined as hypersensitivity reactions, anaphylactic reactions and cytokine release syndrome with onset within 24 hours after the start of an infusion of UCB6114.

All potential infusion-related reactions will be identified programmatically and will then undergo medical review for confirmation based on participant characteristics and other signs and symptoms. The final assessment from the medical review will be used in the programming to ensure that all infusion-related reactions are flagged correctly in the listings and included in the relevant summaries.

Hypersensitivity reactions will be programmatically identified as any TEAE with a PT from both a narrow and broad scope search of category A terms of the ‘Hypersensitivity’ SMQ.

Anaphylactic reactions will be programmatically identified using an algorithmic approach based on the ‘Anaphylactic Reaction’ SMQ. Further details on this algorithm are given in [Section 11](#). Note that if the MedDRA® version is increased from 25.1 during the study, any changes to the terms included in the ‘Anaphylactic Reaction’ SMQ should be applied.

Cytokine release syndrome will be programmatically identified as any TEAE with a PT of ‘Cytokine release syndrome’ from the broad scope search of category A terms of the ‘Hypersensitivity’ SMQ. Since this disorder is characterized by fever, headache, tachycardia, hypotension, rash, tachypnoea and/or hypoxia, a further medical review of participants with these events occurring within 24 hours after infusion of UCB6114 will be performed to confirm any further infusion-related reactions.

Note that any other AEs (i.e. not identified as infusion-related reactions using the rules above) which result in a temporary interruption or permanent discontinuation of a UCB6114 infusion will not be considered as an infusion-related reaction.

8.3 Clinical laboratory evaluations

The use of multiple local laboratories (1 per site in the UK and US) in Part B of this study has meant that results have been recorded in different units and with reference to different normal ranges, and further, for some laboratory tests, different normal ranges have been applied to males and females and age groups. As a first step to ensure comparability of laboratory results, results and normal ranges will be converted to the same International System of Units (SI) units using UCB’s standard conversion factors. This will be programmed at the Study Data Tabulation Model (SDTM) level. Note though that the simple conversion to SI units does not represent a full homogenization of results from different local laboratories using different methods. To ensure full comparability, the observed laboratory results will be normalized to a unique set of standard reference ranges using the location-scale normalization formula (Chuang-Stein, 1992) which normalizes all results in relation to a standard set of reference ranges (for hematology, clinical chemistry and coagulation parameters):

$$s = L_S + (x - L_X) \frac{(U_S - L_S)}{(U_X - L_X)}$$

and when the standard lower limit is 0: $s = x \frac{U_S}{U_X}$ where:

s = normalized observed value

x = original observed value in SI units

L_S = Lower Limit of the reference range chosen to be the standard reference range

U_S = Upper Limit of the reference range chosen to be the standard reference range

L_X = Lower Limit of the reference range associated with the original observed value in SI units (local laboratory reference range)

U_X = Upper Limit of the reference range associated with the original observed value in SI units (local laboratory reference range)

This transformation preserves the distance of the original laboratory result from the lower limit of normal as a multiple of the specified standard reference range.

Note that the choice of the standard reference range is arbitrary, however, the most recent reference ranges used by ICON Central Laboratories (including the age and gender specific reference ranges for parameters, where available) will be used to normalize the results in this study.

Normalization of the laboratory results will be performed in the ADaM programming by ICON.

All normalized laboratory data (hematology, serum chemistry and coagulation) and changes from Baseline for numeric variables will be listed for participants who have at least one value outside of the reference range. All urinalysis data will be listed for all participants. Data will be listed by study participant, laboratory panel, laboratory parameter and visit within each treatment group. Any laboratory measurements that are BLQ or ALQ will be handled as described in [Section 4.2.2](#). For the relevant numeric laboratory parameters, the reference ranges supplied by the local analytical laboratory will be used to flag values outside the reference range as low or high in this listing. For the parameters for which the local laboratory cannot supply the reference ranges, the reference ranges provided by ICON Central Laboratories will be used instead. A listing of all laboratory results outside of the reference range will also be presented. The reference ranges will also be reported in the listings.

In addition, for the relevant hematology, clinical chemistry and coagulation laboratory tests, CTCAE severity grades (Grade 1, Grade 2, Grade 3, Grade 4) will be applied (where possible) in the ADaM programming according to NCI CTCAE Version 5.0, and these grades will also be listed for the relevant laboratory parameters. Note that Grade 0 will be applied in cases where a result is normal for the relevant laboratory test and Grade 5 is not applicable in the grading of laboratory data.

Observed normalized values and changes from Baseline in the hematology, serum chemistry and coagulation parameters presented below in [Table 8-1](#) will be summarized at each visit. In addition, for each of these parameters, the Baseline value, the minimum, maximum, average and last post-Baseline value for each participant will be summarized by cycle using descriptive statistics. These post-Baseline summary measures will be calculated based on all available scheduled postdose values within each cycle, i.e. from Day 8 of the current cycle up to Day 1 (pre-UCB6114) of the subsequent cycle. The last value in a cycle will be the predose value of the subsequent cycle where a subsequent cycle occurs, otherwise it will be the value at the last scheduled assessment. If only one value is available then the average will not be calculated and presented but this value will be used for the minimum, maximum and last post-Baseline summary measures. These summary measures for each cycle will also be listed.

The summaries of normalized hematology, serum chemistry and coagulation values and changes from Baseline will also be presented by Gastric/GEJ-Cancer and CRC tumor type depending on the number of participants with specific tumor types.

For those laboratory parameters with a CTCAE toxicity assigned, shift tables for the change from Baseline in CTCAE severity grade at each visit and to the worst post-Baseline CTCAE severity grade during the Treatment Period will be presented.

Table 8-1: Clinical Laboratory Assessments

Laboratory Assessment	Laboratory Parameters
Hematology	Platelet Count, RBC Count, Hemoglobin, Hematocrit, RBC Indices (MCV, MCH, MCHC), WBC Count with Differential (Absolute Neutrophils, Absolute Lymphocytes, Absolute Monocytes, Absolute Eosinophils, Absolute Basophils)
Clinical Chemistry	ALT, AST, ALP ^a , Bicarbonate, Sodium, Potassium, Magnesium, Chloride, Calcium, Total Bilirubin, BUN or Urea, Serum Creatinine, Glucose (non-fasted), Phosphorus or Phosphate, Albumin, Total Protein, Uric Acid, Amylase, GGT, Cholesterol, Creatine Kinase, CRP, LDH, Lipase, Triglycerides
Coagulation	aPTT and either prothrombin time or INR
Routine Urinalysis	Specific Gravity, pH, Glucose, Protein, Blood, Ketones, Bilirubin, Urobilinogen, Nitrite, Leukocyte Esterase by Dipstick Microscopic Examination (if blood or protein is abnormal, including crystals)
Screening Tests	Pregnancy tests: FSH and estradiol (for women of non-childbearing potential only); serum or urine hCG pregnancy test (for women of childbearing potential) Bone turnover markers: blood BAP, blood CTx, urinary NTx and urinary CTxII Tumor markers: e.g. PSA, CA125, CA19-9

ALP=alkaline phosphatase; ALT=alanine aminotransferase; aPTT=activated partial thromboplastin time; AST=aspartate aminotransferase; BAP=bone alkaline phosphatase; BUN=blood urea nitrogen; CA=cancer antigen; CRP=C-reactive protein; CTx=C-terminal telopeptide; FSH=follicle-stimulating hormone; GGT=gamma glutamyl transferase; hCG=human chorionic gonadotropin; INR=international normalized ratio; LDH=lactate dehydrogenase; MCH=mean corpuscular hemoglobin; MCHC=mean corpuscular hemoglobin concentration; MCV=mean corpuscular volume; NTx=N-terminal telopeptide; PSA=prostate specific antigen; RBC=red blood cell; WBC=white blood cell.

a including liver-specific ALP for use in assessing participants with bone metastases at Screening. In the case of bone metastases liver function abnormalities considered potential Hy's law cases, the liver-specific ALP must be separated from the total in participants with bone metastases and used to assess the liver function instead of the total ALP

The screening laboratory tests included above in [Table 8-1](#) will be listed only.

Liver function abnormalities will be defined using the following criteria:

- ALT or AST $\geq 2 \times \text{ULN}$
- ALT or AST $\geq 3 \times \text{ULN}$
- Total bilirubin $\geq 2 \times \text{ULN}$
- Total bilirubin $\geq 3 \times \text{ULN}$

- ALT or AST $\geq 5\times$ ULN
- ALT or AST $\geq 8\times$ ULN
- ALT or AST $\geq 3\times$ ULN AND total bilirubin $\geq 2\times$ ULN ($>35\%$ direct bilirubin)

For the subgroups of participants with liver metastases and without liver metastases at Baseline, the number and percentage of participants in each liver function abnormality category will be summarized at each visit.

In addition, participants with PDILI criteria are those that fulfill the following laboratory data (based on liver function tests) criteria at a visit:

- AST or ALT and total bilirubin within the normal range at Baseline and AST or ALT $\geq 3\times$ ULN concurrent with total bilirubin $\geq 2\times$ ULN;
- AST, ALT or total bilirubin above ULN at Baseline and AST or ALT ≥ 2 times Baseline values AND AST or ALT $\geq 3\times$ ULN (participants without liver metastases at Baseline)/AST or ALT $\geq 8\times$ ULN (participants with liver metastases at Baseline) concurrent with total bilirubin above ULN at Baseline and total bilirubin ≥ 2 times Baseline value or $\geq 3\times$ ULN (whichever is lower).

All relevant laboratory data collected for participants with a PDILI event (i.e. liver function tests) will be listed at the visits at which at least one of the above criteria was fulfilled.

The number and percentage of participants meeting different combinations of the ALT, AST and total bilirubin criteria defined above will be summarized by treatment group. This summary will be presented for all participants as well as for the subgroups of participants who had liver metastases at Baseline and participants without liver metastases at Baseline.

A separate listing will also be produced containing drug-induced liver injury -relevant family medical history, lifestyle data (alcohol consumption or drug abuse in the previous 6 months), hepatic event supplemental medical history and any hepato-toxic medications taken for participants in the SS with a PDILI event.

